1.1. Background

Chronic Obstructive Pulmonary Disease (COPD) and bronchial asthma (asthma) are common chronic airway diseases that severely impact public health. Globally, approximately 600 million people are affected. In 2015, about 3.2 million people died from COPD worldwide, and 400,000 died from asthma^[1]. In China, chronic airway diseases represented by COPD and asthma have become major chronic conditions seriously endangering the health of the population. Results from the China Pulmonary Health (CPH) study, led by our team, indicate that the prevalence of COPD among people aged 20 and above in China is 8.6%^[2], and the prevalence of asthma is 4.2%^[3]. Chronic airway diseases impose a substantial healthcare burden. However, despite continuously rising medical costs for these diseases, key clinical outcomes have not shown corresponding improvement^[4,5]. Personalized treatment tailored to different patient subtypes is crucial to addressing this dilemma.

It has been established that chronic airway diseases exhibit significant heterogeneity. Different phenotypes exist among asthma patients, such as allergic asthma, late-onset asthma, smoking-related asthma, and obesity-related asthma^[6]. Similarly, COPD patients present with various phenotypes including mild stable, emphysematous type, intermediate type, multiple comorbidities, and multifactorial inflammatory type^[7]. Applying traditional, uniform treatment regimens to different phenotypic patients falls short of meeting the actual needs of disease treatment and management. In clinical practice, there is a need to identify more precise treatable traits for patient classification and personalized management. Several treatable traits beneficial for the individualized management of patients with chronic airway diseases have already been identified, for example, blood eosinophil count^[8] and serum allergen-specific IgE^[9], which have demonstrated clinical utility. There is a pressing need to discover and validate more clinically significant traits to provide a basis for the subsequent implementation of personalized patient management.

1.2. Rationale

Previous research has found that differences in dyspnea perception among populations with chronic airway diseases may lead to different disease outcomes. In asthma patients, approximately 26% of subjects exhibit low dyspnea perception. During follow-up, patients with low perception had higher rates of emergency department visits, hospitalizations, near-fatal asthma attacks, and mortality compared to groups with normal or high perception, suggesting that reduced dyspnea perception may predispose asthma patients to life-threatening acute episodes^[10]. In COPD patients, it has also been observed that after repeated carbon dioxide breathing, patients in the frequent exacerbator group exhibited enhanced dyspnea perception, whereas those in the infrequent exacerbator group showed weakened perception. This mechanism may contribute to the difference in exacerbation frequency between the

two groups^[11]. Consequently, abnormal dyspnea perception may be one of the risk factors leading to refractory chronic airway diseases, and patients with such abnormal perception might represent a novel subtype of chronic airway disease.

However, the influencing factors of dyspnea perception remain unclear. Some studies suggest potential associations with age^[12], gender^[13], airway inflammation^[14], psychological and emotional factors^[15,16]among others. Nevertheless, a comprehensive description of this trait in patients with chronic airway diseases is still lacking, and we do not fully understand the distribution of dyspnea perception and its determinants in this population. This study aims to investigate the distribution and risk factors of abnormal dyspnea perception in patients with chronic airway diseases. By collecting and analyzing other relevant clinical data from these patients, we intend to construct a clinical classification of chronic airway diseases based on dyspnea perception and further identify more treatable traits. The goal is to enable more precise personalized management of patients in clinical practice^[17], addressing the urgent need to reduce the frequency of disease exacerbations, disability, and mortality.

1.3. Study Objectives

This project aims to investigate the distribution of dyspnea perception within established chronic airway disease cohorts from community screenings and hospital-based populations, identify novel subtypes classified by dyspnea perception, analyze their relationships with known biomarkers and other treatable traits, and explore new treatable traits contributing to refractory chronic airway diseases. The findings will provide a foundation for subsequent implementation of personalized management strategies for patients.

2. Study Objectives

2.1. Primary and Quantitative Objectives

Primary Objectives	Quantitative Targets
--------------------	----------------------

 ● To clarify the distribution of dyspnea perception in chronic airway diseases. ● To construct novel subtypes of chronic airway diseases based on the degree of dyspnea perception and analyze their relationship with known biomarkers and other treatable traits. ● To observe the changes in dyspnea perception during follow-up and explore its relationship with outcome measures such as acute exacerbations, occurrence of comorbidities, hospitalizations, and mortality. 	
 ● Complete dyspnea perception measurements in 800 chronic airway disease subjects. ● Complete repeat dyspnea perception measurements one year after baseline in 200 subjects. ● Complete measurements of biomarkers and other treatable traits (e.g., head MRI) in 300 patients. ● Apply for 1-2 patents or software copyrights. ● Publish 2-4 Chinese and English articles; train 4 postgraduate students.
---	---

3. Methods

3.1. Source of Funding

This study is supported by the municipal fiscal science and technology funds, specifically from the Respiratory Institute's Reform and Development Project "Phenotype-based Prognosis and Individualized Diagnosis and Treatment Research for Chronic Airway Diseases."

3.2. Study Design

This is a 3-year observational study. It will involve dyspnea perception measurement, pulmonary function tests, blood sample testing, quality of life assessment, recording of acute exacerbations and comorbidities, and collection of other clinical information in 800 participants with chronic airway diseases. Additionally, 150 normal control subjects will undergo dyspnea perception measurement, pulmonary function tests, blood sample testing, and clinical information collection. Participants with good compliance will undergo regular follow-up, including brain functional magnetic resonance imaging (fMRI) examinations alongside repeated dyspnea perception measurements. The study will analyze the relationship between dyspnea perception and known biomarkers as well

as other treatable traits, aiming to identify new treatable traits underlying refractory chronic airway diseases.

3.3. Study Population:

This study will recruit approximately 800 participants with COPD or asthma and 150 normal control subjects from hospitals and the community. Participants with COPD or asthma will be aged 20-75 years, must meet the diagnostic criteria for COPD according to the 2022 GOLD guidelines or the diagnostic criteria for asthma according to the 2022 GINA guidelines, must be able to participate in the study per protocol, and must provide written informed consent before participating.

1.1.1.1. Inclusion Criteria:

Participants with COPD or asthma must meet all the following criteria:

- Age 20-75 years.
- Meet the diagnostic criteria for COPD according to the 2022 GOLD guidelines
OR meet the diagnostic criteria for asthma according to the 2022 GINA guidelines.
- Agree to participate in the study and provide written informed consent.

Normal control subjects must meet all the following criteria: Age ≥ 20 years; no asthma symptoms and no previous diagnosis of chronic respiratory diseases such as asthma or chronic obstructive pulmonary disease; must provide written informed consent before participation and be able to participate in the study and follow-up per protocol.

1.1.1.2. Exclusion Criteria:

Study participants must not meet any of the following criteria:

- Respiratory tract infection, acute exacerbation of COPD, or acute asthma attack within the past 3 months.
- Presence of other diseases causing substantial lung tissue destruction, such as severe bronchiectasis or tuberculosis.

- History of thoracic or abdominal surgery within the past 3 months.
- Heart rate >120 beats per minute.
- Currently undergoing anti-tuberculosis treatment.
- Presence of other severe, uncontrolled systemic diseases.
- Pregnant or lactating women.

1.1.1.3. 变量及人口学数据 Variables and Demographic Data

1.1.1.4. 暴露 Exposure

The patient's treatment regimen will be determined by their treating physician. No investigational drugs will be administered as part of this study. The study will collect information on the patient's current respiratory medication and specific concomitant medications.

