1.1.1.5. Variables

- Demographic Data: Includes sex, date of birth, height, weight, living environment, education level/years of formal education; smoking history/secondhand smoke exposure history; occupational exposure history; biofuel exposure history.
- Clinical Information: Duration since diagnosis of COPD/chronic bronchitis/emphysema/asthma and age at onset; current respiratory symptoms such as shortness of breath, chest tightness, cough, wheezing, sputum production; past family history; allergy history/atopy.
- Previous Exacerbation History: Exacerbations within the 12 months prior to baseline: number of exacerbations, exacerbation severity (use of systemic corticosteroids/antibiotics/emergency department visit/hospitalization), and length of hospital stay or number of emergency department visit days.
- Comorbidities: Comorbidities present prior to the baseline visit.
- Treatments: Current medications for COPD/asthma/chronic respiratory symptoms (type/duration of use/dosage/frequency), and non-pharmacological treatments; specific concomitant medications (e.g., corticosteroids).
- Pulmonary Function Tests: Spirometry with bronchodilator test; lung volume measurements; diffusing capacity test; fractional exhaled nitric oxide (FeNO) measurement; dyspnea perception measurement.
- Blood Tests: Complete blood count, inhalant allergen screen, total IgE.
- Imaging: Chest HRCT scan (high-resolution computed tomography in inspiratory and expiratory phases).

- Health-Related Quality of Life: Assessed using the COPD Assessment Test (CAT), the Modified British Medical Research Council (mMRC) dyspnea scale, the Asthma Quality of Life Questionnaire (AQLQ), and the St. George's Respiratory Questionnaire (SGRQ).
- Dyspnea Perception Measurement.
- Brain Functional Magnetic Resonance Imaging (fMRI).

4. Data Processing

All statistical analyses will be performed using the Full Analysis Set (FAS), which includes all patients who were enrolled and met the inclusion/exclusion criteria. Missing data will be analyzed as is, without imputation.

The epidemiology and statistics working group at the Chinese Academy of Medical Sciences will perform the statistical analyses using SAS and SUDAAN software.

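### Follow-up, repeat perception testing and fMRI go to an undefined group of good compliers, so the longitudinal primary objective rests on a subset that may not represent the enrolled cohort

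*Protocol*

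**What the plan says.** Section 3.2 (Study Design) fixes who is followed: "Participants with good compliance will undergo regular follow-up". The same sentence places brain fMRI and the repeat perception tests inside that follow-up. It gives no definition or threshold for good compliance, and does not say when or by whom it is judged.

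Section 2.1 lists among the primary objectives: "To observe the changes in dyspnea perception during follow-up and explore its relationship with outcome measures such as acute exacerbations", continuing to comorbidities, hospitalizations and mortality. Its quantitative targets are:

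- baseline: "Complete dyspnea perception measurements in 800 chronic airway disease subjects"
- repeat: "Complete repeat dyspnea perception measurements one year after baseline in 200 subjects"
- deeper phenotyping: "Complete measurements of biomarkers and other treatable traits (e.g., head MRI) in 300 patients"

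Section 4 (Data Processing) bases all analyses on a full analysis set of every eligible enrolled patient and adds: "Missing data will be analyzed as is, without imputation". The outcome models named there are linear or logistic regression with multivariate analysis.

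On outcome recording, section 3.2 includes exacerbations and comorbidities among the items collected in the 800. The variable list (section 1.1.1.5) describes exacerbations only for the year before baseline and comorbidities only as present before the baseline visit.

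**The concern.** The third primary objective is longitudinal, and the protocol selects the people who can answer it by their behaviour. Nobody needs to intend a bias for this to matter. Patients who are sicker at entry, or who become ill, may find visits harder to keep. Patients who feel little breathlessness may see less reason to return. Either would make the followed group differ from the 800 in the quantities the objective is about.

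Three results are exposed: the event risks during follow-up, the mean one-year change in perception, and the association between perception and outcome. Section 1.2 motivates the study with abnormal perceivers and their worse course, so thinning out such patients would weaken the comparison of most interest.

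This is a sampling rule written into the protocol. A later analysis plan can adjust for it in part, but it cannot supply measurements that were never taken.

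**Working it through.** **1. The plan's own figures.** The targets in section 2.1 carry no effect size, alpha, power or dropout rate, so they cannot be derived; only their ratios can be formed.

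- Planned one-year repeat: 200/800 = 25%, so 600/800 = 75% have no planned repeat.
- Biomarkers and other traits, with head MRI as the example: 300/800 = 37.5%.
- Followed for clinical outcomes: not stated. The 200 cannot stand in for it, because section 3.2 places fMRI inside the same follow-up and the target that names head MRI is 300.

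**2. Timing of the compliance judgement.** There are two readings, and the protocol does not choose between them.

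- Judged at baseline: events cannot cause exclusion, but the group may still differ in baseline prognosis and perception.
- Judged during follow-up: an exacerbation, admission or death can itself remove a patient.

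**3. Effect on event risk (illustration).** Let p be the true risk and r the selection probability of patients with a future event relative to those without. The risk in the subset is pr/(pr + 1 − p). Assume p = 0.25:

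| r | risk in subset |
|---|---|
| 1 | 0.25 |
| 0.8 | 0.200/0.950 = 0.21 |
| 0.67 | 0.1675/0.9175 = 0.18 |
| 0.5 | 0.125/0.875 = 0.14 |

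**4. Effect on the association (illustration).** Observed odds ratio = true odds ratio × selection odds ratio, where the latter is r among low perceivers divided by r among the others. Assume true risks of 35% (low perception) and 20% (others): (0.35/0.65)/(0.20/0.80) = 2.15.

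| r, low perceivers | r, others | observed odds ratio |
|---|---|---|
| 0.67 | 0.67 | 2.15 |
| 0.5 | 0.5 | 2.15 |
| 0.67 | 1 | 2.15 × 0.67 = 1.44 |
| 0.5 | 1 | 2.15 × 0.5 = 1.08 |
| 1 | 0.67 | 2.15/0.67 = 3.2 |

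The odds ratio is spared when selection on the outcome is equal in both perception groups. It moves only when selection depends jointly on perception and outcome, and then it can move either way. In the rows with equal selection the event risks are still wrong.

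**5. What the analysis text does about it.** With missing values left as they are, a regression that needs the repeat test runs on patients who have one, whatever the nominal analysis set. Its coefficients are protected if selection depends only on baseline variables in the model. Unweighted means and event risks are not.

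**6. Outcome recording.** Section 3.2 can be read as recording exacerbations and comorbidities in all 800. Section 1.1.1.5 limits both to the time before baseline and lists neither post-baseline hospitalization nor vital status. Together the two sections do not show for whom post-baseline outcomes will exist.

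**The case against.** The best defence has four parts.

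- A deeply measured subset is ordinary in an observational cohort, and 200 is not wrong in itself. This stands; the objection is to how the subset is chosen.
- The objective is worded as observing and exploring, the analysis is mainly descriptive, and the first two primary objectives rest largely on baseline data. This also stands, and it limits the damage to the third objective.
- Section 4 excludes imputation but not weighting, and an analysis plan that is not at hand may provide it. So the absence of an adjustment is not held against the protocol. The selection rule is in the protocol and remains.
- Outcomes may be recorded in all 800, and relating baseline perception to outcomes needs no repeat test. Section 3.2 leaves that possible, but section 1.1.1.5 does not secure it. Change in perception needs the repeat test in any case.

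A reader might also infer stronger claims, which the protocol does not support:

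- **That three quarters of the cohort has no follow-up.** The 200 is the target for repeat perception tests only.
- **That the study loses a known amount of power.** With 26% low perceivers (section 1.2, an asthma figure), assumed risks of 35% and 20% and two-sided 5%, power is 58% with 200 followed, 75% with 300 and 99% with 800. Which figure applies depends on a number the protocol does not give.
- **That results will describe compliant survivors.** This requires compliance to be judged after events can occur, and the time of judgement is not given.
- **That the association is attenuated because low perceivers drop out.** Step 4 shows that the direction depends on the assumed pattern. Section 1.2 reports worse outcomes with low perception in asthma, but enhanced perception among frequent exacerbators in COPD.

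**Conclusion.** The concern holds in a limited form. Followed as written, section 3.2 answers a primary objective in a group chosen by an undefined behavioural criterion, with repeat measurements planned for 25% of the patients. Event risks and mean change may therefore not represent the enrolled cohort, and the perception-outcome association may be biased if selection depends jointly on perception and outcome.

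That compliance is related to prognosis and perception is a plausible inference and is not stated in the protocol. Neither the size nor the direction of bias can be computed from it. The risk, odds-ratio and power figures above rest on assumed inputs and show only what such selection could do. The change is worth making because it is cheap, not because a particular bias has been shown.

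**What to change.** 1. **Section 3.2:** delete the compliance condition. Invite the repeat-test and fMRI subset at random from all consenting patients, within strata of disease (COPD, asthma) and baseline perception, for example thirds. If strata are invited at different rates, carry the known rates into the analysis as weights.
2. **Section 4:** compare baseline characteristics of patients with and without repeat data. Weight the longitudinal analyses by the inverse probability of being re-measured, modelled on baseline variables already collected, and show the unweighted result beside it.
3. **Sections 3.2 and 1.1.1.5:** reconcile them by stating that post-baseline exacerbations, comorbidities, hospitalizations and deaths are recorded for all 800 where existing contacts or records allow, and report how many patients that covers.

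Steps 1 and 2 cost a few sentences, a sampling list and one additional model. More than 200 must be invited to obtain 200 repeats: at an assumed completion of 80% or 60%, 200/0.8 = 250 or 200/0.6 = 334. Completion may be somewhat lower than among chosen compliers. Random invitation does not prevent later refusal or dropout, and weighting corrects for these only as far as baseline variables explain them. Any repeats already obtained under the present rule need step 2 most, since random invitation can apply only to those still to come. New telephone contact with everyone outside the subset would go further than step 3, but it costs more and this recommendation does not depend on it.

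### Control eligibility ignores the spirometry already planned and has no upper age limit, so people with undiagnosed airflow obstruction, or older than any eligible patient, can be enrolled as normal controls

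*Protocol*

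**What the plan says.** All the eligibility text is in the Protocol, section 3.3 Study Population and the Inclusion and Exclusion Criteria beneath it.

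- **Recruitment:** "This study will recruit approximately 800 participants with COPD or asthma and 150 normal control subjects from hospitals and the community".
- **Control age:** "Normal control subjects must meet all the following criteria: Age ≥ 20 years". No upper limit follows.
- **Control health status:** "no asthma symptoms and no previous diagnosis of chronic respiratory diseases such as asthma or chronic obstructive pulmonary disease". Consent and ability to take part are the only other conditions.
- **Patient age:** "Participants with COPD or asthma will be aged 20-75 years".
- **Patient diagnosis:** the participant must meet the 2022 GOLD criteria for COPD or the 2022 GINA criteria for asthma. A previous diagnosis is not required.
- **Exclusions for all participants:** the nearest to undiagnosed lung disease is "Presence of other diseases causing substantial lung tissue destruction, such as severe bronchiectasis or tuberculosis". None sets a lung-function or age threshold.
- **Tests in controls (3.2 Study Design):** "150 normal control subjects will undergo dyspnea perception measurement, pulmonary function tests, blood sample testing, and clinical information collection". The Variables section describes the pulmonary function tests as including spirometry with a bronchodilator test, and also lists respiratory symptoms, sex and date of birth.
- **Analysis set (4. Data Processing):** the Full Analysis Set, "which includes all patients who were enrolled and met the inclusion/exclusion criteria".

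The Protocol gives no rule for a control whose spirometry shows obstruction.

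**The concern.** A group called normal should not be able to contain the disease under study. Here it can, because the controls' disease-free status rests on diagnostic history and on symptoms of asthma alone, while the patients' status rests on diagnostic criteria. The two sets of criteria therefore overlap. A person with obstruction who has never been diagnosed and reports no asthma symptoms satisfies both, and nothing in the text says to which group that person belongs. Meeting the control criteria is also enough to be kept, so the analysis set as described would not remove such a person later.

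The age ranges differ as well. The Protocol's Rationale names age and gender among the factors that may influence dyspnea perception, yet controls may be older than any eligible patient. Above 75 there are no patients with whom to compare them.

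What is at stake is any contrast of patients with controls and, if the controls serve as a reference for abnormal perception, the position of that limit.

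**Working it through.** The Protocol gives no derivation for the 150 controls and no cut-off for abnormal perception, so there is no stated figure to reproduce. The check is a reading of the criteria, followed by an illustration of scale.

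**Step 1. Do the criteria overlap?** Take a 60-year-old recruited from the community with airflow obstruction meeting the GOLD criteria, no asthma symptoms, no previous diagnosis and none of the listed exclusions.

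- Patient criteria: age within 20-75, GOLD criteria met, consent given. Eligible.
- Control criteria: age at least 20, no asthma symptoms, no previous diagnosis, consent given. Eligible.

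The overlap follows from the text and needs no assumption about numbers.

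**Step 2. How many such controls?** The Background section states that "the prevalence of COPD among people aged 20 and above in China is 8.6" percent. Let u be the share of COPD that is undiagnosed. The Protocol does not give u, so it is varied. Diagnosed cases are removed by the control criterion, so among the people who remain the COPD share is

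p = 0.086u / (1 − 0.086(1 − u)),

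and the expected number among controls is 150p.

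| u (assumed) | p | 150p |
|---|---|---|
| 25% | 0.0215/0.9355 = 2.3% | 3.4 |
| 50% | 0.0430/0.9570 = 4.5% | 6.7 |
| 75% | 0.0645/0.9785 = 6.6% | 9.9 |
| 90% | 0.0774/0.9914 = 7.8% | 11.7 |
| 100% | 0.0860/1 = 8.6% | 12.9 |

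The chance of at least one, 1 − (1 − p)^150, is 97% at u = 25% and higher for every larger u. This assumes that controls resemble the general population aged 20 and above, and that the asthma-symptom criterion removes none of the cases.

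**Step 3. What would that do to a percentile limit, if one were taken from the controls?** Let unaffected controls follow N(0,1) and a fraction p follow N(d,1). The limit x solves (1 − p)Φ(x) + pΦ(x − d) = 0.05 or 0.95. Without contamination the limits are ±1.645. The size and sign of d are assumed.

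| Shift d of affected controls | 5th percentile, p = 2.3% to 8.6% | 95th percentile, p = 2.3% to 8.6% |
|---|---|---|
| −2 SD | −1.78 to −2.18 | 1.63 to 1.60 |
| −1 SD | −1.69 to −1.81 | 1.63 to 1.61 |
| −0.5 SD | −1.66 to −1.71 | 1.64 to 1.62 |
| +0.5 SD | −1.64 to −1.62 | 1.66 to 1.71 |
| +1 SD | −1.63 to −1.61 | 1.69 to 1.81 |
| +2 SD | −1.63 to −1.60 | 1.78 to 2.18 |

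The limit on the side of the shift moves outward by 0.02 SD (1.66 − 1.645) to 0.54 SD (2.18 − 1.645). The opposite limit moves by at most about 0.04 SD.

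For comparison, the sampling standard error of an empirical 5th percentile from 150 normal observations is √(0.05 × 0.95/150)/φ(1.645) = 0.0178/0.103 ≈ 0.17 SD. Shifts of 0.5 SD in affected controls move the limit by less than half of that. Shifts of 2 SD with high contamination move it by about three times as much.

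**Step 4. Controls over 75.** No age distribution is given, so their number cannot be computed.

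**The case against.** Four points can fairly be made on the other side.

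**The controls' role.** A reader might infer that these 150 people define normal perception, and so that the first primary objective is biased. The Protocol does not say this. That objective concerns the distribution in chronic airway diseases, and the subtypes rest on the degree of perception. Neither mentions controls or a percentile. A reference role is likely, since controls are the only group without known disease, but it remains an inference. This objection stands.

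**Size and direction of bias.** A reader might take the 26% low-perception share in asthma quoted in the Rationale and conclude that it would be reported as about 12%. If patients follow N(m,1) with 26% below −1.645, then m = −1.645 + 0.643 = −1.002. A limit of −2.18 gives Φ(−1.18) ≈ 12%. That requires all COPD to be undiagnosed and affected controls to lie 2 SD lower. With a 0.5 SD downward shift the 26% becomes 24-25%; with an upward shift it becomes 26-27%. The Rationale describes both enhanced and weakened perception in COPD, so no direction can be assumed, and the 26% is not said to come from a 5th-percentile rule. This objection also stands.

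**Recoverability.** Spirometry, symptoms, sex and date of birth are collected, so obstructed or over-75 controls could be identified and handled in analysis. That limits the damage and shows that it is too strong to say every patient-control comparison is confounded: no such comparison is specified, and a missing age cap does not by itself show that the age distributions differ. But the stated eligibility rule still admits these people, and removing them afterwards would depart from it.

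**Symptoms.** The term asthma symptoms may well be read to cover dyspnea, wheeze, chest tightness and cough, so a visibly symptomatic smoker might be turned away. The firm gap is obstruction without such symptoms.

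A reader might also infer from the patient-only wording of the analysis set that controls enter no analysis. That is a loose word rather than a plan to discard them.

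**Conclusion.** The point holds as a defect of the eligibility criteria. They permit undiagnosed obstruction and people over 75 in the normal control group, they overlap with the patient criteria, and they leave the planned lung-function results without any bearing on eligibility. This rests on the text alone.

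The numerical consequence is less certain. About 3 to 13 of 150 controls is an order of magnitude that depends on an assumed undiagnosed share and on controls resembling the general population. The resulting distortion has no known direction and runs from negligible to about half an SD at a percentile limit, if such a limit is used at all. The documents do not support a claim that the share of patients with abnormal perception will be understated. Severity: should be fixed, and easily fixed.

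**What to change.** Amend the control criteria in the Inclusion Criteria to:

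1. require no airflow obstruction on the spirometry already planned, by the same 2022 GOLD definition that is used for patients;
2. require no chronic respiratory symptoms, rather than no asthma symptoms only;
3. set control age to 20-75, as for patients.

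State also what the controls are for, and adjust patient-control comparisons for age and sex. Both are already in the list of variables.

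The cost is protocol wording plus the replacement of the screened controls found to have obstruction: roughly 2-9% under the assumptions above, or 3 to 13 people per 150 screened. No new measurement is needed, provided that the controls' pulmonary function tests include the bronchodilator test named in the Variables section; the amendment should say so.

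Frequency matching on age and sex is optional and would affect recruitment. Rewording the analysis set to name patients and controls is optional too, and costs nothing.

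### Baseline perception is tested only after three event-free months, but the one-year repeat carries no such condition, so a recent exacerbation or infection can be read as change in the trait

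*Protocol*

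**What the plan says.** The exclusion criteria (1.1.1.2, under section 3.3) open with "Study participants must not meet any of the following criteria" and list "Respiratory tract infection, acute exacerbation of COPD, or acute asthma attack within the past 3 months" first. The rule appears nowhere else, so it governs entry.

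The repeat test is described in two places. Section 2.1 gives the target: "Complete repeat dyspnea perception measurements one year after baseline in 200 subjects". Section 3.2 says who is followed: "Participants with good compliance will undergo regular follow-up, including brain functional magnetic resonance imaging (fMRI) examinations alongside repeated dyspnea perception measurements". Neither mentions clinical state at the repeat, a visit window or postponement.

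The third primary objective in section 2.1 is "To observe the changes in dyspnea perception during follow-up and explore its relationship with outcome measures such as acute exacerbations", followed by further outcomes.

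On data capture, section 3.2 provides for "recording of acute exacerbations and comorbidities". The variable list (1.1.1.5) gives detail only for history: "Exacerbations within the 12 months prior to baseline: number of exacerbations, exacerbation severity". It has no follow-up item for respiratory infections that fall short of an exacerbation. The Full Analysis Set in section 4 is the one "which includes all patients who were enrolled and met the inclusion/exclusion criteria", so it depends on eligibility at entry and not on state at the repeat.

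**The concern.** The two measurements that form the change score are taken under different conditions. The condition that differs, a recent exacerbation, is one of the outcomes to which the change is to be related. If a recent event shifts measured perception for a time, two artefacts follow with a constant trait: a non-zero mean change, and a correlation between change and exacerbation count. Neither can be told apart from a real change without knowing when the last event occurred.

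The protocol gives some ground for expecting such an effect. Section 1.2 lists airway inflammation among the possible influences on perception. The study also aims to build subtypes on perception, and the repeat is its only evidence on whether perception is stable over a year. A repeat that mixes acute state with trait weakens that evidence.

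**Working it through.** The protocol derives no figure for the 200 repeats, so there is none to reproduce. The calculation below shows how large the problem could be.

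**Inputs from the protocol.** 200 repeats; a three-month (0.25-year) event-free period before baseline. I take the baseline test to be done at entry.

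**Inputs assumed, because the protocol gives none.**
- Mean exacerbation rate m of 0.5, 1 or 2 per patient-year.
- Rates that vary between patients as a gamma distribution with shape 1.5.
- A shift in perception of 0.5 SD, in one direction, after an event in the previous three months.

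**Share of repeats within three months of an event.** Let b = 1.5/m. A patient who enters with no event in the previous 0.25 year has a rate that is gamma with shape 1.5 and rate parameter b + 0.25. Therefore

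P(event in the 0.25 year before the repeat) = 1 − [(b + 0.25)/(b + 0.5)]^1.5

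- m = 0.5, b = 3: 1 − (3.25/3.5)^1.5 = 0.105; × 200 = 21
- m = 1, b = 1.5: 1 − (1.75/2)^1.5 = 0.182; × 200 = 36
- m = 2, b = 0.75: 1 − (1/1.25)^1.5 = 0.285; × 200 = 57

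The corresponding share at baseline is zero by design. Infections without exacerbation would add to these counts. At a low rate of 0.2 per year the share is only about 5%.

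**Bias in the mean change** = share × shift: 0.105 × 0.5 = 0.05 SD; 0.182 × 0.5 = 0.09 SD; 0.285 × 0.5 = 0.14 SD.

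**Spurious association.** A simulation used the same rate model, a constant trait and a change score with noise SD 0.8. The correlation of change with first-year exacerbation count was 0.10, 0.13 and 0.15 at the three rates for a 0.5 SD shift. For shifts of 0.3 to 1.0 SD it ran from 0.06 to 0.27. With 200 pairs, a correlation reaches two-sided 5% significance at about 0.139. When repeats within three months of an event were left out, the correlation fell to about zero. In this model, then, the unequal condition is the whole source of the association.

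**The case against.** The case against has several parts.

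- **Exacerbations are recorded.** A reader might infer that the study collects nothing on exacerbations during follow-up. That is not so: section 3.2 provides for recording them, and the detailed item in 1.1.1.5 is headed as previous history and does not limit later recording. If dates are captured, time since the last exacerbation can be derived. What remains is that no date is specified and that infections without exacerbation are not covered, although the entry rule treats both alike.
- **The protocol does not order testing just after an event.** A reader might infer that it does. The one-year timing stands in a column of quantitative targets, beside patents and publications, and nothing forbids postponement. This stands. Equally, nothing asks for postponement, so sites may act differently.
- **Analysis choices belong in the analysis plan.** Adjustment and flagging can be left there. The condition of the test and the date of the last event cannot, because they must be fixed before the visit and cannot be recovered afterwards.
- **Change around exacerbations may be of interest.** The objective is exploratory and does not restrict change to a stable-state trait. This is fair. It is a reason to keep recent-event repeats and identify them, since without that the two kinds of change cannot be separated.
- **The shift is assumed.** Section 1.2 speaks only of potential associations with airway inflammation and gives no size or direction for a post-event shift. Shifts in mixed directions would partly cancel in the mean. This stands in full.

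**Conclusion.** The asymmetry is real and bears on a primary objective: baseline is restricted to stable patients and the repeat is not. A recent event can be read as change in the trait, and can produce a change-exacerbation association when the trait is constant.

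A reader might infer that it will be read that way. The protocol does not support that, because exacerbations are to be recorded and a regression could allow for them.

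The size is unknown. On the assumptions above, about 10% to 28% of repeats are affected and the mean change is biased by about 0.05 to 0.14 SD. A plain Poisson calculation, 1 − exp(−m/4), would suggest 12%, 22% and 39% (24, 44 and 79 of 200). It ignores both the variation between patients and the fact that the entry rule favours those with lower rates, so the lower figures are the ones to use. The spurious correlations are small, and at a 0.5 SD shift only that for the highest rate exceeds the 5% threshold. The correction is worth making because it is cheap and must come before the repeat visits.

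**What to change.** In section 3.2, state that the three-month condition from the exclusion criteria also applies to the repeat perception test, with a window after month 12 so that a patient with a recent event can be tested later. A window of three months would cover a single event just before month 12. It fits the stated timeline: last enrolment in December 2025 plus 15 months is March 2027, before the last visit in December 2027.

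In 1.1.1.5, add the date of the last respiratory infection or exacerbation, recorded at the repeat.

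Keep and flag repeats that still fall within three months of an event. Report the change analysis with and without them, or adjusted for time since the last event. Excluding them from the main analysis is not advised: it selects on the outcome and would remove frequent exacerbators first, the patients most relevant to refractory disease.

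The cost is a short amendment and one case report form item. Some repeats will come later than 12 months, so the interval between tests will vary a little.
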